2.1 Safety Assessments

The safety assessments include the following:

- Adverse Events (AEs)
- Safety Labs (Chemistry, Hematology and Coagulation, Urinalysis, urine drug screen, and additional tests listed in Appendix 2 of the protocol.)
- Best Corrected Visual Acuity (BCVA)
- Visual Field
- Ishihara Color Vision Test
- Slit Lamp Biomicroscopy
- Intraocular Pressure (IOP)
- Dilated Fundoscopy
- Physical Exam
- Body weight and height for body mass index (BMI)
- Vital Signs
- Electrocardiograms (ECG)
- Pregnancy Test

CONFIDENTIAL

The contents of this document are confidential to [REDACTED]
Unauthorized use, disclosure, or reproduction is strictly prohibited.

2.2 Statistical Hypotheses

The primary clinical endpoint will be assessed using a one-sided Fisher's exact test at a 0.10 significance level. This analysis combines the 600 mg and 300 mg Q4W treatment arms ("pooled group") and compares them to placebo.

- Null Hypothesis (H_0): At Week 37, the percentage of patients showing a proptosis response in the study eye without deterioration in the fellow eye and separately in either eye is less than or equal in the LASN01 pooled group (300 mg and 600 mg) compared to placebo.
- Alternative Hypothesis (H_1): At Week 37, this percentage is greater in the LASN01 pooled group compared to placebo.

3. Study Design and Procedures

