6.1 Unit of Analysis

The unit of analysis in this study will be the study eye and either eye for all appropriate ophthalmic summaries. The study eye is determined by the PI or designee as the more severely affected eye at Week 1 (Day 1) before dosing. This will be based on the severity of proptosis in both eyes. If both eyes are

CONFIDENTIAL

The contents of this document are confidential to [REDACTED]
Unauthorized use, disclosure, or reproduction is strictly prohibited.

affected equally, the principal investigator (PI) or designee will select the study eye and may take into account other factors such as the CAS. If both proptosis and CAS are equal, the PI or designee will select the study eye and may consider other factors for disease severity per their expert judgement. Both eyes will be assessed for efficacy and safety at designated study visits, but the study eye will be used to assess the primary clinical endpoint. If only one eye is determined to meet the eligibility criteria, that is the study eye by default.

The non-study eye will be referred to as the fellow eye. Fellow eye safety summaries will also be presented as appropriate.

Either eye for responder analyses is defined as the eye that meets responder criteria in either eye (study eye or fellow eye) at Week 37 (Day 253) and the same eye will be analyzed at each visit. If both eyes meet the responder criteria at Week 37 (Day 253) the study eye will be the eye to use in either eye analyses at each visit.

Either eye for continuous Total CAS analyses is defined as the eye that achieves the largest reduction in Total CAS at Week 37 (Day 253), and this single eye will be used for analyses at all visits. If both eyes demonstrate an equal reduction in Total CAS at Week 37 (Day 253), the study eye will be used as the either eye. As a single eye per patient per visit will be analyzed and that eye is held constant for all visits, no additional considerations are needed to account for multiple eyes within a patient.

Non-ocular AEs and medical history will be presented at the patient level.

For ECG and vital sign data that is measured in triplicate, the average of available readings will be the unit of analysis.

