6.3 Data Analysis Conventions

Ora will perform all data analyses described in this SAP using [REDACTED]. Outputs will be provided in RTF for tables and figures, and in PDF for tables, listings, and figures (TLFs) in landscape orientation. Each formal TLF deliverable will include three combined PDF files, one for each of the output types.

Data will be summarized and listed separately. Continuous variables will be summarized using the number of patients (n), mean, standard deviation (SD), median, minimum, and maximum. Additionally, coefficient of variation (CV%), geometric mean and geometric CV% will be provided for PK concentrations and parameters (except for T_{max}). Values of 0 will be considered missing when calculating the geometric means. Categorical data will present counts and percentages within each category. Standard Error (SE) may be added to continuous efficacy outputs for Total CAS. Individual patient data listings will also be produced. For all other parameters except for PK concentrations and PK parameters, minima and maxima will retain the same precision as raw values; means and medians will have one additional decimal place; SDs will have two additional decimal places. For PK concentrations and parameters except n, all other descriptive statistics will be presented with the same number of significant digits as raw PK concentrations (3 significant figures). Percentages will be rounded to one decimal place (e.g., XX.X%). Differences between active treatment and placebo will be calculated as Active – Placebo, and change from baseline as Follow-up Visit – Baseline.

Unless otherwise specified, all statistical tests will be one-sided at a significance level of $\alpha=0.1$. Confidence intervals (CIs) for differences between treatment arms will be two-sided at 95% confidence unless stated otherwise. All p-values will be rounded to four decimal places; p-values less than 0.001 will be shown as "<0.001," and those greater than 0.9999 as ">0.999."

Summaries will be presented by treatment arm, including 300 mg, 600 mg, pooled treatment group (300 mg and 600 mg) for efficacy, placebo arm, [REDACTED] and, where appropriate, by visit and eye (study eye and either eye). Where possible, p-values will be displayed for comparisons of relevant active treatment groups to placebo; [REDACTED]. Listings will be presented by patient number, treatment arm, visit, time point, and parameter as applicable based on enrolled patients unless otherwise specified.

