6.4 Adjustments for Multiplicity

As this is an early-phase proof-of-concept study, there is no strong control of the family-wise error rate ($\alpha = 0.1$), and there are no multiplicity adjustments for the primary or secondary efficacy endpoints.

7. Disposition of Patients

Patient disposition will be presented in terms of the number of patients who were randomized to masked study medication [REDACTED], with subcategories of treated patients. The number and percentages of patients will be summarized for the analysis populations including the Efficacy, Safety, PK, and PD Populations. Number and percentage of patients who completed the study and discontinued from the study will be summarized. Patients who are not discontinued from the study will be considered study completers. Number and percentage of patients who completed treatment and discontinued the treatments early will be summarized. Completing treatment will be based on the patients' most recent consented protocol version. Disposition will be summarized by treatment arm, including LASN01 300 mg, LASN01 600 mg, placebo, [REDACTED], and overall for all patients. Percentages will be calculated using randomized (or enrolled patients) as the denominator unless otherwise specified.

The reasons for premature study discontinuation and treatment discontinuation will be summarized by treatment arm and overall for all discontinued patients. Percentages will be calculated using discontinued patients as the denominator. The reasons for study discontinuation that will be summarized include: Death, Lost to Follow-up, Physician Decision, Protocol non-compliance with protocol procedures, Study Termination, Withdrawal of Consent, and Other. The reasons for treatment discontinuation that will be

CONFIDENTIAL

The contents of this document are confidential to [REDACTED]
Unauthorized use, disclosure, or reproduction is strictly prohibited.

summarized include: Adverse Event, Non-compliance with study drug administration or other protocol procedures, Physician Decision, Pregnancy, Prohibited Concomitant Medication, Study Termination, Withdrawal of Consent, and Other. A patient listing will be provided that includes the date of and reason for premature study and treatment discontinuation.

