11.1 Analysis of Primary Efficacy Endpoint(s)

The primary efficacy endpoint is the percent of patients showing a response in proptosis measured using Hertel exophthalmometer (≥ 2 mm decrease from baseline) in the study eye and separately in either eye without increased proptosis (≥ 2 mm increase) in the other eye at Week 37 (Day 253) as measured by Hertel Exophthalmometer. The primary efficacy endpoint will be assessed with a one-sided Fisher's exact p-value comparing the pooled active group to placebo at each visit, including the primary endpoint visit at Week 37. Interpretation of statistical significance should be made at the $\alpha=0.1$ level. Two-sided 95% CIs for responder analyses may be calculated with the Clopper-Pearson exact method.

Fisher's exact test syntax:

```
Proc sort data = <data>;
    by TRTPN descending AVALC; *orders the responses;
run;

proc freq data=<data> order=data; *Keeps the order in the dataset;
    tables TRTPN*AVALC / fisher;
run;

where TRTPN is planned treatment (1=Active and 2=Placebo)
```

CONFIDENTIAL

The contents of this document are confidential to [REDACTED]
Unauthorized use, disclosure, or reproduction is strictly prohibited.

AVALC is the responder variable (Y = response in proptosis of ≥ 2 mm decrease from baseline in the study eye and separately in either eye and < 2 mm increase in the other eye; and N = response of < 2 mm decrease from baseline in the study eye and separately in either eye or ≥ 2 mm increase in the other eye).

Note: with the above ordering, the right-sided p-value will be the correct one-sided p-value from Fisher's exact test for the primary hypothesis.

The primary efficacy analysis will utilize the Efficacy Population with LOCF. Additional sensitivity analysis may be conducted on the primary efficacy endpoint with observed data only (ODO) using study eye.

The percentage of proptosis responders by treatment arm (pooled active group and placebo) over time through Week 37 using line graphs for the Efficacy Population with LOCF will be produced for study eye and either eye separately.

Tables and figures will be provided for the individual treatment groups and pooled active group for all available visits while Week 37 remains the primary endpoint.

. A listing of proptosis in both eyes will be provided.

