Due to several consent withdrawals and patients declining to re-consent for the 12-month extension, the Sponsor unmasked the clinical team to assess whether early study termination was appropriate. Investigators, the CRO clinical operations team, and CRO statisticians remained masked until the database lock. The following specific changes have been made and the additions are considered exploratory:

- Due to early termination of the study, only proptosis measured by Hertel and Total CAS will be analyzed in tables. Other secondary and exploratory endpoints will be listed.
- Either eye responder analyses have been added for proptosis by Hertel and Total CAS, and either eye continuous analyses have been added for Total CAS. Either eye responder and continuous Total CAS analyses will identify an eye at Week 37 (Day 253) and use that same eye in the analysis for each visit.
- A sensitivity analysis, as defined in protocol Section 9.2.4, has been added for Total CAS in the study eye and separately for either eye. Only the pooled active group will be compared to placebo. The sensitivity analysis of the primary responder rate for proptosis from protocol Section 9.4.2. has been removed.

CONFIDENTIAL

The contents of this document are confidential to [REDACTED]
Unauthorized use, disclosure, or reproduction is strictly prohibited.

- An ANCOVA model has been added to existing mean and mean change from baseline Total CAS tables. The model includes baseline and treatment as factors and will be run separately for each eye (study eye and either eye) and visit. Only the pooled active group will be compared to placebo.
- 95% CI for proptosis responder analysis has been removed
- LOCF has been added as the imputation method for missing data for all efficacy analyses.
- Per Protocol Population analyses have been removed.
- ODO analyses have been added for all proptosis and CAS tables to check robustness of results.

17. References

1. Giner G, Smyth GK (2016). statmod: probability calculations for the inverse Gaussian distribution. R Journal 8(1), 339-351.
2. ICH Harmonised Tripartite Guideline: Statistical Principles for Clinical Trials E9. International Council for Harmonisation of Technical Requirements for Pharmaceuticals for Human Use. 05 February 1998.

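### The SAP contradicts itself on the primary endpoint: three sections make study eye and either eye both primary with no deciding rule, while two others say the study eye decides and the either-eye addition is exploratory

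*SAP*

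**What the plan says.** **Both eye definitions as primary.** The primary efficacy row of SAP Section 2 names the study eye and, separately, either eye. Section 2.2 puts both into one null hypothesis, "a proptosis response in the study eye without deterioration in the fellow eye and separately in either eye", tested "at a 0.10 significance level". Section 11.1 defines the primary endpoint as response "in the study eye and separately in either eye without increased proptosis" in the other eye, and its responder variable (AVALC) carries both definitions. Section 6.3 adds that, unless otherwise specified, "all statistical tests will be one-sided at a significance level of" 0.1. Section 6.4 says "there are no multiplicity adjustments for the primary or secondary efficacy endpoints".

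**Study eye as primary.** SAP Section 6.1 says "the study eye will be used to assess the primary clinical endpoint". The protocol agrees in Sections 3, 8.1 and 9.2.3.1. It lists either-eye responder analyses of TED-related clinical parameters only among exploratory endpoints (Sections 3 and 9.2.4).

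**Status and background of the change.** SAP Section 16 reports that "the Sponsor unmasked the clinical team to assess whether early study termination was appropriate", and that investigators, CRO clinical operations and CRO statisticians stayed masked until database lock. It continues: "The following specific changes have been made and the additions are considered exploratory". Either-eye responder analysis of Hertel proptosis is on that list.

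**Secondary endpoints.** The secondary proptosis responder endpoints in SAP Section 2 are written for either eye only. Protocol Section 3 writes them for the study eye.

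**The concern.** A primary endpoint should identify one result that answers the primary question. Here a reader holding Sections 2, 2.2 and 11.1 would expect two primary p-values. A reader holding Sections 6.1 and 16 would expect one. The protocol cannot break the tie, because SAP Section 1 says the SAP's methods supersede it.

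If the two tests disagree, the plan gives no means of saying whether the trial met its primary endpoint. That matters more than usual because Section 16 attributes the changes to the sponsor, and its clinical team had seen treatment assignments. If the choice between the two definitions is still open on paper, or was made with unmasked data in view, the p-value of the chosen test no longer has its stated meaning, and no alpha adjustment repairs that.

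**Working it through.** **Inputs from the documents.** Pooled LASN01 n = 16, placebo n = 8; one-sided Fisher's exact test at 0.10; planning rates 65% v 15%, or 65% v 10% (SAP Section 4, protocol Section 9.5).

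**Assumptions, not in the documents.** Change in each eye is normal with SD 1.5 mm; between-eye correlation is 0.3 to 0.7; both eyes have the same distribution; arms do not differ under the null.

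**Step 1: reproduce the stated power.** Power is the sum, over all 17 × 9 outcomes (a, b) with Fisher p ≤ 0.10, of Bin(a; 16, p_A) × Bin(b; 8, p_P).
- 65% v 15%: 81.8% (SAP: about 81%).
- 65% v 10%: 89.7% (SAP: about 90%).

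The plan's figures reproduce for a single test.

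**Step 2: true size of the study-eye test alone.** The same sum with p_A = p_P gives 0.68% at a common 15% rate and 2.67% at 25%. The largest value at any common rate is 5.6%. The test is well below its nominal 10%.

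**Step 3: how little separates the two definitions.** The one-sided p is the hypergeometric tail with both margins fixed.
- 7/16 v 1/8: [C(16,7)·C(8,1) + C(16,8)·C(8,0)] / C(24,8) = (91,520 + 12,870) / 735,471 = 0.142.
- 8/16 v 1/8: [C(16,8)·C(8,1) + C(16,9)·C(8,0)] / C(24,9) = (102,960 + 11,440) / 1,307,504 = 0.087.

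One active patient who responds only in the fellow eye, with no such gain on placebo, changes the result from not significant to significant.

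**Step 4: false success if either test counted.** The mean change is set so that P(change ≤ −2 mm) equals the stated rate. Each simulated trial applies the Step 3 test to both definitions.

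| Common rate per eye | Study eye alone | At least one of the two |
|---|---|---|
| 15% | 0.7% | 2.4–3.2% |
| 25% | 2.7% | 5.5–6.5% |

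A wider grid, with unequal rates between eyes and correlations of 0 or 0.5, gave at most about 8.9%. The two sizes cannot sum to more than 2 × 5.64% = 11.3%, so 10% is not a proven ceiling, but no scenario tried reached it.

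**Step 5: effect of the fix on power.** With the study eye as sole primary at one-sided 0.10, power stays at the 81.8% of Step 1.

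**The case against.** The best defence is that this is a wording slip in a terminated, signal-seeking trial. The word separately can mean separate reporting. Sections 6.1 and 16 supply a hierarchy, Section 6.4 openly disclaims strong error control, and Section 1 gives a reason for looking at both eyes that does not depend on the data: the drug is given systemically. All of this supports reporting either-eye results. None of it explains why either eye stands inside the primary hypothesis, and a disclaimer of error control does not say which test is primary.

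Several stronger readings are tempting, and the documents do not carry them.

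- **That either eye was demonstrably added after unmasking.** Section 16 dates neither event. The contents page lists a version history, but it is not in the text available for review. The order is a strong inference, because the list of changes follows directly from the unmasking and termination account. Against it, the protocol already had either-eye responder analyses as exploratory. What appears new is their explicit use for Hertel proptosis and their place beside the primary. The masked parties also included the CRO statisticians.
- **That the SAP permits success on either test.** It states no such rule; it only fails to exclude it.
- **That the error rate doubles to 19–20%.** Those are nominal bounds (1 − 0.9² = 19%; 0.10 + 0.10 = 20%). The actual figures are far lower, because Fisher's test is conservative here and the two tests overlap.
- **That fellow-eye changes are mostly measurement noise.** The documents give no Hertel error figure, and under masked assessment noise would affect both arms.
- **That the 81% power is wrong.** The SAP ties it to 65% v 15% and never claims it for the either-eye test.

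**Conclusion.** The contradiction is established from the text: Sections 2, 2.2 and 11.1 on one side, Sections 6.1 and 16 and the protocol on the other. It sits in the primary hypothesis, so it should be resolved before results are interpreted.

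The error inflation is modest in absolute terms: to about 2–3% at a 15% rate and about 5.5–6.5% at 25%. In relative terms it is roughly two- to five-fold (5.5/2.7 ≈ 2.0; 3.2/0.68 ≈ 4.7). These figures depend on the assumed correlation and on both eyes behaving alike. If fellow eyes respond less often, the two tests overlap more and the inflation shrinks.

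The weightier concern is a possibly data-informed choice of which result is the primary one. The simulation does not measure that, and the undated account in Section 16 neither confirms it nor rules it out.

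**What to change.** 1. Remove the either-eye wording from the primary endpoint in SAP Section 2, from the null hypothesis in Section 2.2, and from the primary definition in Section 11.1, including AVALC.
2. State once that study-eye response at Week 37, pooled LASN01 versus placebo, is the only test that decides the primary hypothesis.
3. Define a separate either-eye responder variable. Keep its tables and figures in a subsection labelled exploratory.
4. Restore the study eye in the secondary proptosis responder endpoints in Section 2, with either eye as exploratory.
5. Give in Section 16 the date of the sponsor unmasking and the date of each endpoint change. If the dates show that the change came first, the unmasking concern falls away; the contradiction still needs correcting.

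Cost: SAP wording, plus one separately named variable. No either-eye output is lost and no power is lost on the study-eye test. The sponsor gives up one possible route to a positive primary result.

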3.1 General Study Design

This proof-of-concept Phase 2 study comprises the randomized, double-masked, placebo-controlled treatment arms in patients with TED with no prior anti-IGF-1R treatment [REDACTED]

[figure not shown]
The randomized treatment arms will be used to evaluate the efficacy, safety, tolerability, PK, immunogenicity, and PD properties of 2 dose levels (300 and 600 mg) of LASN01 administered IV Q4W 7 to 13 doses in anti-IGF-1R-naïve patients with TED. [REDACTED]

The general study design for treatment-naïve patients is depicted in Figure 1 for the European protocol version 7.1 and the randomized treatment-naïve patients in the United States protocol version 7.0.

CONFIDENTIAL

The contents of this document are confidential to [REDACTED]
Unauthorized use, disclosure, or reproduction is strictly prohibited.

Figure 1. General Study Design for Treatment-Naïve Patients

Following 49 weeks of dosing (last dose administered on Day 337), patients will be followed for an additional 24 weeks for a total study duration of 73 weeks (End of Study [EOS] visit on Day 505 ±7 days).

Study participation (Baseline to the EOS visit) will require approximately 505 days, not including the Screening period. The Screening visit will occur up to 30 days before Day 1.

Treatment assignments will be performed centrally by [REDACTED]

A Safety Review Committee (SRC) will be formed to periodically review safety and available PK and PD data. For the randomized, double-masked treatment arms, the SRC will examine masked data. The first data review will occur after at least six patients have been treated and followed for six weeks. Subsequent meetings may take place every 12 months, depending on enrollment rates and SRC discussions. The SRC Charter outlines the committee's structure and provides further conduct details. A separate SRC shell will be created to document and confirm SRC outputs.

Interim analysis (IA) may be performed when at least 50% of evaluable patients in the randomized treatment arms complete at least 8 weeks in the study. [REDACTED] The IA will include both masked and unmasked outputs for Sponsor review. A separate unmasked statistician

CONFIDENTIAL

The contents of this document are confidential to [REDACTED]
Unauthorized use, disclosure, or reproduction is strictly prohibited.

and a separate unmasked programming team will produce unmasked outputs. Designated Lassen Senior Management personnel who are not responsible for study management or decisions that impact data integrity, in accordance with relevant study plans, will review unmasked interim data.

Following initial analysis of efficacy, the Sponsor may also expand the enrollment in the current cohorts and/or initiate additional cohorts with different subpopulations of TED patients (e.g., chronic disease, recurrence following previous treatment, or in addition to standard of care). An amendment to the protocol will be submitted for appropriate regulatory authority review and/or approval in such a case.

Study visits will be referred to in all tables and listings as the scheduled week (e.g., Week 2) corresponding to the visit to enable reviewers to understand the assessment timing without referring to the protocol visit schedule.

